## 2. PROTOCOL SUMMARY

### 2.1. Synopsis

PRODUCT NAME/NUMBER	Varespladib-methyl
PROTOCOL NUMBER	OPX-PR-02
DEVELOPMENT PHASE	2
PROTOCOL TITLE	A Phase 2, Randomized, Double-blind, Placebo-controlled Study to Evaluate the Safety, Tolerability, and Efficacy of Varespladib in Patients Hospitalized with Severe COVID-19 Caused by SARS-CoV-2
INDICATION	Severe coronavirus disease 2019 (COVID-19)
STUDY POPULATION	Adult participants aged 18 to 80 years diagnosed with severe laboratory-confirmed COVID-19 caused by severe acute respiratory syndrome coronavirus 2 (SARS-CoV-2)
OBJECTIVES	
The objectives of this study are as follows:
 
Primary:
 
 
• To evaluate the safety, tolerability, and efficacy of varespladib in patients hospitalized with severe COVID-19 when given in addition to the institutional standard of care
 
 
Secondary:
 
 
• To evaluate the efficacy of varespladib in reducing the need for respiratory support
 
• To evaluate the efficacy of varespladib in reducing the duration of hospitalization
 
• To evaluate the efficacy of varespladib in improving time to recovery
 
• To evaluate time to resolution of symptoms
 
• To evaluate the efficacy of varespladib in reducing the incidence of morbidity and mortality
 
 
Exploratory:
 
 
• To assess the pharmacokinetics (PK) of varespladib in COVID-19 patients
 
• To evaluate the overall effect of varespladib in suppression of secretory phospholipase A2 (sPLA2) with SARS-CoV-2 infection
 
• To assess pharmacoeconomic outcomes
 

STUDY DESIGN	
This is a 2-part, multi-center, randomized, double-blind, placebo-controlled, phase 2 study designed to evaluate the safety, tolerability, and efficacy of oral varespladib, in addition to standard of care, in patients hospitalized with severe COVID-19 caused by SARS-CoV-2.
 
The goals of this study are to define a safe dose for the population and to assess the safety, tolerability, and efficacy of orally dosed varespladib to improve survival without respiratory failure in patients hospitalized with severe COVID-19 when given in addition to the institutional standard of care therapy.
 
The mortality rates of COVID-19 are strongly linked to acute respiratory distress syndrome (ARDS) which is correlated with elevations of sPLA2 and widespread loss of functioning lung tissue. Upregulation of sPLA2 has been shown to be involved in the dysregulated inflammatory cascade pathways (increased markers of immune activation, also known as cytokine release syndrome) and enzymatic degradation of lung surfactant linked to the development of ARDS. It is believed that treatment with

varespladib, a potent inhibitor of sPLA2, will prevent or mitigate progression of pulmonary dysfunction in COVID-19 patients by two mechanisms: suppression of sPLA2-induced inflammation and, uniquely, preservation of pulmonary surfactant by direct inhibition of the enzyme responsible for surfactant phospholipid degradation: sPLA2.
Data from previous phase 2 clinical trials of varespladib suggest it was capable of reducing mortality in severely septic patients with ARDS, particularly when treatment was initiated within 18 hours of identification of organ failure.
The study will be conducted in 2 parts. Both parts will be randomized and double-blind. Part 1 will be dose-finding in 4 parallel treatment groups randomized to treatment with varespladib (at 250 mg once daily [QD], twice daily [BID], or three times daily [TID] [250, 500, or 750 mg/day]) or placebo in a 5:5:5:3 ratio. After all participants in Part 1 have completed Day 28, a data safety monitoring board (DSMB) will review results from Part 1, including all available safety data through Day 60, and will recommend the dose regimen to be used in Part 2. Part 2 will randomize an additional 72 participants to the dose regimen selected from Part 1 or placebo in a 1:1 ratio.
In both parts of the study, eligible participants will be enrolled and randomized to receive active varespladib or placebo in addition to institutional standard of care for 7 days (7 complete days of study drug administration after randomization).
Participants will be assessed daily per standard of care while hospitalized and on a regular basis after discharge. The Day 1, 4, 7, 14, and 28 visits will be performed in person (either at the hospital/site or via a home health provider) to assess safety, obtain blood and urine samples for laboratory tests, and obtain clinical outcome data. The Day 2, 3, 5, 6, 8, 9, 10, 11, 12, 13, 15, 16, 17, 18, 19, 20, 21, 45, and 60 visits for discharged participants may be conducted by phone or via electronic patient-reported outcome (ePRO) devices.
Efficacy will be assessed by respiratory failure-free survival at Day 28. Safety will be assessed by evaluating adverse events (AEs), vital sign measurements, use of oxygen therapies, changes in levels of biomarkers, clinical laboratory test results, electrocardiograms (ECGs), physical examination findings, and concomitant medications and therapies. A DSMB will evaluate safety data at specified intervals during both parts of the trial.
Pharmacokinetic samples will be drawn from all participants in Part 1 and in a subset of approximately 14 participants in Part 2 in order to enable estimation of PK parameters in approximately 22 participants receiving active treatment with varespladib. The pharmacokinetic characterization of drug concentrations for each dose to be profiled will use noncompartmental analysis. Standard PK parameters assessed will include measures of the extent of absorption using estimates of the area-under-the-curve (AUC) and rate-of-absorption using the maximum concentration ( $C_{max}$ ) and the time of $C_{max}$ ( $T_{max}$ ).

PLANNED NUMBER OF PARTICIPANTS	Approximately 90 participants will be enrolled. Part 1 of the study will enroll 18 participants; Part 2 of the study will enroll approximately 72 participants in a 1:1 ratio.
STUDY ENTRY CRITERIA	
Inclusion criteria:
 
 
1. Participant is hospitalized with severe COVID-19 illness, defined in accordance with the FDA Guidance for Industry – COVID-19: Developing Drugs and Biological Products for Treatment or Prevention (May 2020):             
 
a. Severe illness: 
 
i. Symptoms suggestive of severe systemic illness with COVID-19, which could include any symptom of moderate illness or shortness of breath at rest, or respiratory distress
 
ii. Clinical signs indicative of severe systemic illness with COVID-19, such as respiratory rate <math>\geq 30</math> per minute, heart rate <math>\geq 125</math> per minute, <math>\text{SpO}_2 \leq 93\%</math> on room air at sea level or partial pressure of oxygen <math>\text{PaO}_2/\text{fraction of inspired oxygen FiO}_2 < 300</math>
 
 
 
2. Participant has a positive virologic nucleic acid amplification test (NAAT) indicating SARS-CoV-2 infection in a sample collected <math>< 72</math> hours prior to randomization.
 
3. Participant is between the ages of 18 and 80 years at the time of enrollment.
 
4. Participant (or legally authorized representative) provides informed consent prior to initiation of any study procedures.
 
5. Participant agrees to not participate in another clinical trial for the treatment of COVID-19 or SARS-CoV-2 through Day 28.
 
6. Participant has adequate hematologic status (in the absence of transfusion and growth factor support for at least 28 days), defined as follows:             
 
a. Absolute neutrophil count (ANC) <math>\geq 1.5 \times 10^9/\text{L}</math>
 
b. Platelet count <math>\geq 75 \times 10^9/\text{L}</math>
 
c. Hemoglobin <math>\geq 9 \text{ g/dL}</math>
 
 
 
7. Participant has an Eastern Cooperative Oncology Group (ECOG) performance score of 0-2.
 
 
Exclusion criteria:
 
 
1. Participant has mild, moderate, or critical COVID-19 defined in accordance with the FDA Guidance for Industry:             
 
a. Mild COVID-19: 
 
i. Symptoms of mild illness with COVID-19 that could include fever, cough, sore throat, malaise, headache, muscle pain, gastrointestinal symptoms, without shortness of breath or dyspnea
 
ii. No clinical signs indicative of moderate, severe, or critical severity
 
 
 
b. Moderate COVID-19: 
 
i. Symptoms of moderate illness with COVID-19, which could include any symptom of mild illness (fever, cough, sore throat, malaise, headache, muscle pain, gastrointestinal symptoms) or shortness of breath with exertion
 
ii. Clinical signs suggestive of moderate illness with COVID-19, such as respiratory rate <math>\geq 20</math> breaths per minute, peripheral oxygen saturation (<math>\text{SpO}_2</math>) <math>> 93\%</math> on room air at sea level, heart rate <math>\geq 90</math> beats per minute
 
iii. No clinical signs indicative of severe or critical illness
 
 
 
 
 
 


	
c. Critical COVID-19:
 

i. Respiratory failure defined based on resource utilization requiring at least one of the following:

• Endotracheal intubation and mechanical ventilation

• Oxygen delivered by high-flow nasal cannula ([HFNC] heated, humidified, oxygen delivered via reinforced nasal cannula at flow rates > 20 L/min with fraction of delivered oxygen <math>\geq 0.5</math>)

• Noninvasive positive pressure ventilation

• extracorporeal membrane oxygenation (ECMO), or

• Clinical diagnosis of respiratory failure (i.e., clinical need for one of the preceding therapies, but preceding therapies not able to be administered in setting of resource limitation)

ii. Shock (defined by systolic blood pressure <math>< 90</math> mmHg, or diastolic blood pressure <math>< 60</math> mmHg or requiring vasopressors)

iii. Multi-organ dysfunction/failure

 

2. Participant has taken investigational medications within 7 days or 5 half-lives prior to enrollment, whichever is shorter.

3. Participant has required any new form of sedation, anxiolysis or central nervous system (CNS) depressant within the 48 hours prior to enrollment that would interfere with neurologic assessments at enrollment.

4. Has history of cerebrovascular accident or intracranial bleeding of any kind, acute coronary syndrome, myocardial infarction, or severe pulmonary hypertension.

5. Participant has chronic respiratory failure not associated with COVID-19, defined as prior need for home oxygen, need for home noninvasive positive-pressure ventilation (NIPPV) for reasons other than isolated sleep apnea, or other signs of chronic respiratory failure, in the investigator's judgment.

6. Upper gastrointestinal (GI) bleed evidenced by hematemesis, "coffee-ground" emesis or nasogastric aspirate, or hematochezia thought to originate from upper GI tract.

7. Participant has abnormal liver function defined as any 2 of the following at screening:

a. Total bilirubin <math>\geq 2 \times</math> ULN

b. Alanine aminotransferase (ALT) <math>\geq 3 \times</math> ULN

c. Aspartate aminotransferase (AST) <math>\geq 3 \times</math> ULN

d. Alkaline phosphatase (ALP) <math>> 3 \times</math> ULN

e. Gamma-glutamyl transferase (GGT) <math>> 3 \times</math> ULN

8. Participant has an estimated glomerular filtration rate (eGFR) <math>< 60</math> mL/min.

9. Participant has a known allergy or significant adverse reaction to varespladib-methyl or related compounds.

10. Participant is considered by the investigator to be unable to comply with protocol requirements due to geographic considerations, psychiatric disorders, or other compliance concerns; or has any serious medical condition or clinically significant laboratory, ECG, vital sign, or physical examination abnormality that would prevent study participation or place the participant at significant risk, as judged by the Investigator.

11. Participant is breast-feeding, pregnant, has a positive serum hCG pregnancy test, or is not willing to use a highly effective method of contraception for 14 days after treatment. Highly effective methods of contraception are as follows:

--	--

	
 
a. Combined (estrogen- and progestogen-containing) hormonal contraception associated with inhibition of ovulation (oral, intravaginal, or transdermal)
 
b. Progestogen-only hormonal contraception associated with inhibition of ovulation (oral, injectable, or implantable)
 
c. Intrauterine device, intrauterine hormone-releasing system
 
d. Bilateral tubal occlusion
 
e. Vasectomized partner
 
f. Sexual abstinence
 
g. Double-barrier method (condoms, sponge, diaphragm, with spermicidal jellies, or cream)
 

INVESTIGATIONAL PRODUCTS (IP)	
Test: varespladib-methyl (LY333013) 250 mg immediate-release, oblong, white, film-coated tablet for oral administration
 
LY333013 contains the excipients anhydrous lactose USP/National Formulary (NF), lactose monohydrate USP/NF, hydroxypropyl cellulose USP/NF, polysorbate 80 (vegetable source) USP/NF, microcrystalline cellulose USP/NF, croscarmellose sodium USP/NF, magnesium stearate (vegetable source) USP/NF, and the film coat Opadry II 85F18422 White.
 
Reference: placebo
 
Oral formulation matched to the oral varespladib tablet.

TREATMENT REGIMENS	
Varespladib or placebo will be administered in addition to institutional standard of care for 7 days.
 
Part 1: Participants will be randomized to receive varespladib (250 mg QD, BID, or TID [250, 500, or 750 mg/day]) or placebo in a 5:5:5:3 ratio.
 
Part 2: Participants will be randomized to receive varespladib or placebo in a 1:1 ratio. The varespladib dose for Part 2 will be the dose selected from Part 1.
 
The written institutional standard of care at each site may change during the study. Other COVID-19 treatments currently approved or authorized for emergency use by the FDA are permitted if in the institution's written standard of care.

PLANNED STUDY SITES	
Approximately 5 to 10 study sites in the United States.

CRITERIA FOR EVALUATION	
Efficacy endpoints:
 
Primary efficacy endpoint:
 
 
• Proportion of participants alive and free of respiratory failure at Day 28 (respiratory failure is defined in exclusion criterion 1.c.i)
 
 
Secondary efficacy endpoints:
 
 
• Clinical improvement as measured by the World Health Organization (WHO) 9-point ordinal scale from baseline through Day 60
 
• Time to and proportion of subjects with all-cause mortality through Day 60
 
• Proportion of participants who experienced respiratory failure within the first 28 days after randomization
 
• Among patients that never experience respiratory failure in the first 28 days, time to initiation, duration, and proportion of subjects receiving supplemental oxygen or other respiratory support within the first 28 days after randomization
 
• Among patients that experience respiratory failure in the first 28 days, time to initiation and duration of the forms of respiratory support meeting criteria outlined in critical COVID criteria (exclusion criteria 1.c.i) within the first 28 days after randomization
 

	
 
Number of days of oxygen support through Day 28 after randomization
 
SpO2 through Day 28 after randomization
 
Number of ventilator-free days through Day 28 after randomization
 
Number of hospitalization days through Day 28 after randomization
 
Number of days without renal stabilization and/or replacement through Day 28 after randomization
 
Number of organ failure-free days through Day 28 after randomization
 
Number of days at elevated level of care (intensive care unit [ICU]) through Day 28 after randomization
 
Number of healthcare encounters through Day 28 after randomization
 
 
Exploratory endpoints:
 
 
sPLA2 within blood samples from treatment initiation to Day 28 after randomization
 
 
Safety and tolerability endpoints:
 
 
Incidence and severity (based on National Cancer Institute [NCI] Common Terminology Criteria for Adverse Events [CTCAE] v5.0 grade) of AEs, serious AEs, and AEs leading to discontinuation of IP
 
Vital signs
 
Changes in levels of biomarkers: cardiac troponin, C-reactive protein, and ferritin
 
Clinical laboratory evaluations
 
12-lead ECGs
 
 
PK endpoints (exploratory):
 
 
PK parameters
 
 
Pharmacoeconomic endpoints (exploratory):
 
 
Selected secondary endpoints to include number of healthcare encounters, number of hospitalization days, and number of days at elevated level of care (ICU), after randomization through Day 28.
 

STATISTICAL METHODS	Descriptive statistics (n, mean, median, standard deviation [SD], minimum, and maximum for continuous data; frequencies and percentages for categorical data) will be used to summarize study data and details of analyses as outlined in the study Statistical Analysis Plan (SAP). Quantitative outcomes (i.e., durations of interventions or healthcare events, ordinal scales, SpO 2 , and concentrations) will generally be analyzed via ANCOVA models for change from baseline. Dichotomous outcomes (i.e., occurrence of interventions or healthcare events) will generally be analyzed with logistic regression models, with risk differences presented and calculated via the delta method. Time-to-event outcomes (i.e., mortality, time till interventions or healthcare events) will generally be analyzed with Cox proportional hazards models. These analyses will control for covariates to be specified in the SAP. Pharmacokinetic and biomarker data will be summarized descriptively. Further details and specifications are provided in the SAP.
SAMPLE SIZE DETERMINATION	A total of approximately 90 participants will be randomized, 18 in Part 1 and 72 in Part 2. This is an exploratory proof of concept study and is not powered based on statistical assumptions.
STUDY AND TREATMENT DURATION	
The overall study duration is expected to be approximately 18 months (6 months of active enrollment and 2 months of follow-up in Part 1; 2 to 4 weeks for DSMB review of Part 1 results at Day 28 and selection of the Part 2 dose; 6 months of active enrollment in Part 2; and 2 months of follow-up in Part 2).
 
The sequence and approximate duration of the study periods will be as follows:

	

1. Screening: up to 72 hours

2. Treatment: 7 days

3. Follow-up: 28 days after randomization

4. Safety follow-up: 45 and 60 days after randomization

 
The maximum study duration for each participant is approximately 60 days.
 
The treatment duration for each participant is 7 days from the point of randomization (7 complete days of study drug administration after randomization). Screening/enrollment and baseline (Day 1) of the Treatment Period can take place on the same day if the required screening test results are available.

--	--

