## 7.2. Rationale and Discussion of Study Design

The available nonclinical and clinical data are sufficient to support a small, phase 2, proof-of-concept trial in adult participants with COVID-19. The initial dose-ranging part of the study will be used to select the safest dose that is likely to demonstrate clinical efficacy in Part 2 of the study and later trials. Safety reviews of data from Part 1 and interim data from Part 2 are designed to ensure participant safety prior to enrollment and treatment of a substantial number of participants.

The use of a placebo control will enable interpretation of safety and efficacy data. The study design requires that both treatment arms (varespladib and placebo) receive standard of care concurrently. Thus, participants will receive treatment in a timely manner while being evaluated for the potential clinical benefit of varespladib.

This study is designed to exclude as few potentially critically ill COVID-19 patients as possible. However, restricting the study population to severe patients and excluding the critical population will better enable interpretation of safety and toxicity data. In addition, excluding patients who already meet clinical criteria of chronic respiratory failure or who already require oxygen support will allow for clearer measurement of progression of acute respiratory failure and consistency with our underlying hypothesis.

Given the safety concern for cerebrovascular accidents (CVA) and myocardial infarction (MI) due to COVID-19, patients at risk of CVA and acute coronary syndrome (ACS) are excluded, and patients requiring any form of sedation, anxiolysis, or central nervous system (CNS) depressant within the 48 hours prior to enrollment that would interfere with neurologic assessments at enrollment are excluded. Given the known modest, transient increases in liver enzymes with varespladib, patients with liver abnormalities are excluded. Given the predominantly renal clearance of varespladib, patients with renal insufficiency are excluded.

The efficacy endpoints for this study were selected to demonstrate superiority of varespladib over placebo. The primary endpoint was selected to evaluate clear clinical benefit based on survival without respiratory failure, whereas secondary and exploratory endpoints were selected to evaluate a range of potential effects of varespladib over the course of treatment that may inform later trials.

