5. Participant has chronic respiratory failure not associated with COVID-19, defined as prior need for home oxygen, need for home noninvasive positive-pressure ventilation (NIPPV) for reasons other than isolated sleep apnea, or other signs of chronic respiratory failure, in the investigator's judgment.
6. Upper gastrointestinal (GI) bleed evidenced by hematemesis, "coffee-ground" emesis or nasogastric aspirate, or hematochezia thought to originate from upper GI tract.

7. Participant has abnormal liver function defined as any 2 of the following at screening:
  - a. Total bilirubin  $\geq 2 \times$  ULN
  - b. Alanine aminotransferase (ALT)  $\geq 3 \times$  ULN
  - c. Aspartate aminotransferase (AST)  $\geq 3 \times$  ULN
  - d. Alkaline phosphatase (ALP)  $> 3 \times$  ULN
  - e. Gamma-glutamyl transferase (GGT)  $> 3 \times$  ULN
8. Participant has an estimated glomerular filtration rate (eGFR)  $< 60$  mL/min.
9. Participant has a known allergy or significant adverse reaction to varespladib-methyl or related compounds.
10. Participant is considered by the investigator to be unable to comply with protocol requirements due to geographic considerations, psychiatric disorders, or other compliance concerns; or has any serious medical condition or clinically significant laboratory, ECG, vital sign, or physical examination abnormality that would prevent study participation or place the participant at significant risk, as judged by the Investigator.
11. Participant is breast-feeding, pregnant, has a positive serum hCG pregnancy test, or is not willing to use a highly effective method of contraception for 14 days after treatment.  
Highly effective methods of contraception are as follows:
  - a. Combined (estrogen- and progestogen-containing) hormonal contraception associated with inhibition of ovulation (oral, intravaginal, or transdermal)
  - b. Progestogen-only hormonal contraception associated with inhibition of ovulation (oral, injectable, or implantable)
  - c. Intrauterine device, intrauterine hormone-releasing system
  - d. Bilateral tubal occlusion
  - e. Vasectomized partner
  - f. Sexual abstinence
  - g. Double-barrier method (condoms, sponge, diaphragm, with spermicidal jellies, or cream)

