### **9.5. Discontinuation of Study Intervention**

#### **9.5.1 Individual Participant Halting Criteria**

If a clinically significant finding is identified (including, but not limited to, deterioration from baseline) after enrollment, the investigator or qualified designee will determine if any change in participant management is needed. Every effort should be made to administer the planned doses. Dosing should be held for a participant who experiences any of the following toxicities:

- Any Grade  $\geq 2$  creatinine increase ( $> 1.5 \times$  baseline or ULN)
- Any new, treatment-emergent occurrence of any of the following adverse events of special interest:

- Cerebrovascular accident
- Acute coronary syndrome
- Supraventricular arrhythmia requiring urgent medical intervention
- Any ventricular tachycardia/fibrillation including Torsade de Pointes
- Hepatic toxicity with AST and/or ALT  $\geq 3 \times$  ULN for 2 days or  $> 5 \times$  ULN on one occasion

If a participant becomes unable to swallow the IP due to worsening of their condition, nasogastric administration or a dose delay may be considered in consultation with the medical monitor. In general, treatment with IP should continue for the full 7 days unless the participant is unable to continue treatment or if it is the participant's best interest to discontinue treatment. If a participant must discontinue IP, every effort will be made to continue the participant in the study through Day 60. If a participant experiences an SAE judged to be related to the IP, the treatment for that participant will be permanently discontinued from the IP, but every effort will be made to continue the participant in the study through Day 60.

Any new clinically relevant adverse finding will be reported as an adverse event (AE) as defined in [Section 11.1](#).

Discontinuation from IP does not mean discontinuation from the study, and remaining study procedures should be completed as indicated by the study protocol.

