### **9.5.2 Management of Acute Kidney or Liver Injury**

Acute kidney/liver injury has been reported as a possible complication during the disease progression of COVID-19.

Extra caution and monitoring will be exercised when treating patients with COVID-19-induced hepatic dysfunction. Given the relatively short duration of treatment (7 days) compared to previous studies with varespladib and the transient nature of hepatic enzyme elevation, subjects with acute liver injury will continue IP and be closely monitored with clinic visits and repeated blood work including liver function tests on Days 14 and 28. If hepatic enzymes exceed the hepatic toxicity limits specified in [Section 9.5.1](#), IP should be discontinued. However, every effort will be made to continue the participant in the study through Day 60.

In the event of acute kidney injury secondary to COVID-19, the subsequent dose of the study drug will be withheld and will be recommenced once renal parameters become normal and an interval of at least 5 hours is available before the next dose. Once recommenced, IP will be given through the original 7-day treatment period and the missed dose will not be taken. If renal function is persistently abnormal and the participant misses study drug more than 24 hours, their IP treatment should be discontinued.

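### Exclusion 7 sets no single-enzyme ALT/AST cap, so an isolated value above 5 × ULN is numerically eligible although 9.5.2 discontinues drug if it persists on treatment; that hepatic limit also carries two actions (hold in 9.5.1, discontinue in 9.5.2)

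*Protocol*

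**What the plan says.** **Entry.** Exclusion 7 appears in the Synopsis and again in Protocol 8.2.2: "Participant has abnormal liver function defined as any 2 of the following at screening". The five tests are total bilirubin ≥ 2 × ULN, ALT ≥ 3 × ULN, AST ≥ 3 × ULN, ALP > 3 × ULN and GGT > 3 × ULN. No other criterion names a liver test. Exclusion 10 is a general clause. It covers, among other things, a "clinically significant laboratory, ECG, vital sign, or physical examination abnormality that would prevent study participation" or puts the participant at significant risk, in the investigator's judgement.

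**Intent.** Protocol 7.2 explains the liver exclusion: "Given the known modest, transient increases in liver enzymes with varespladib, patients with liver abnormalities are excluded". The same section says that the study tries to exclude as few potentially critically ill patients as possible.

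**On treatment.** Protocol 9.5.1, which concerns findings after enrollment, says: "Dosing should be held for a participant who experiences any of the following toxicities". One entry reads "Any new, treatment-emergent occurrence of any of the following adverse events of special interest", and the list after it ends with "Hepatic toxicity with AST and/or ALT" at ≥ 3 × ULN for 2 days or > 5 × ULN once. Protocol 9.5.2 refers back to those limits: "If hepatic enzymes exceed the hepatic toxicity limits specified in" 9.5.1, then "IP should be discontinued. However, every effort will be made to continue the participant in the study through Day 60". Short of the limits, participants with acute liver injury stay on drug under close monitoring.

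**The concern.** The entry rule counts abnormal tests; the on-treatment rule looks at the height of one enzyme. The two do not meet. One aminotransferase can be raised to any height and still count as a single abnormality. A patient can therefore satisfy every numeric criterion at a value that the protocol treats, during dosing, as a reason to end treatment. Section 7.2 does not say why an isolated rise of any size would be acceptable.

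The second issue does not depend on that pattern. Any participant who crosses the hepatic limit on study meets one instruction in 9.5.1 and another in 9.5.2. Two sites could handle the same result differently, and a site that follows 9.5.1 is not told how a hepatic hold ends.

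At stake are the safety of a patient who starts a drug with known enzyme increases from an already high value, early stops that an entry cap would avoid, and uniform handling across sites.

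**Working it through.** The plan gives no figure to reproduce on this point. The check is logical, with a little arithmetic.

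**Step 1. Which profiles pass exclusion 7?** In multiples of ULN, the rule excludes when

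I(bilirubin ≥ 2) + I(ALT ≥ 3) + I(AST ≥ 3) + I(ALP > 3) + I(GGT > 3) ≥ 2.

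Five yes/no tests give 2^5 = 32 patterns. Those with a sum of 0 or 1 number 1 + 5 = 6, so 32 − 6 = 26 are excluded. Two of the six that pass are isolated ALT and isolated AST. These counts show the structure of the rule, not how common any pattern is.

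| Bilirubin | ALT | AST | ALP | GGT | Sum | Exclusion 7 | Above 5 × ULN? |
|---|---|---|---|---|---|---|---|
| 1 | 5.1 | 1 | 1 | 1 | 1 | passes | yes |
| 1 | 10 | 2.9 | 1 | 1 | 1 | passes | yes |
| 1 | 20 | 2.9 | 3 | 3 | 1 | passes | yes |
| 1 | 2.9 | 5.1 | 3 | 3 | 1 | passes | yes |
| 1.9 | 4 | 2.9 | 1 | 1 | 1 | passes | no |
| 1 | 3 | 3 | 1 | 1 | 2 | excluded | no |

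ALT at 20 × ULN with AST at 2.9 passes, while ALT and AST both at 3 × ULN are excluded.

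**Step 2. When would the stop apply?** Protocol 10.2.2 lists no chemistry on Day 1. The scheduled on-drug chemistry is on Days 4 and 7. The liver tests that 9.5.2 names, on Days 14 and 28, come after dosing ends on Day 7 or 8. For a participant who starts with a full Day 1 and is still above 5 × ULN:

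- stopped after the Day 4 doses: 3/7 = 43% of dosing days lost;
- stopped before the Day 4 doses: 4/7 = 57%;
- stopped before the Day 7 doses: 1/7 = 14%.

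**Step 3. One limit, two actions.**

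| | 9.5.1 | 9.5.2 | Restart rule |
|---|---|---|---|
| Creatinine / kidney injury | hold | withhold, then discontinue if more than 24 hours of drug are missed | yes, once renal parameters are normal |
| Hepatic limit | hold | discontinue | none |

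For the kidney, the two sections form a sequence. For the liver they do not, because nothing links the hold to the discontinuation.

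**Step 4. Raised baselines.** Section 9.5.2 refers only to exceeding the limits and does not repeat the qualifier about new, treatment-emergent events. Whether that qualifier governs the hepatic line in 9.5.1 is unclear, because bullet nesting is lost in the text available. Neither section says what to do with an enzyme already raised at entry. The fifth profile in the table (ALT 4) shows why this matters for the remedy. If baseline elevations simply count, a stable ALT of 4 × ULN meets the limit of ≥ 3 × ULN for 2 days, and 9.5.2 discontinues drug with no change in the patient.

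**Step 5. Who is affected?** SAP Section 10 reports Part 1 complete with 18 participants and one participant recruited to Part 2. At most 72 − 1 = 71 remain, if Part 2 resumes and fills. The documents give no rate for isolated ALT or AST above 5 × ULN, so no expected count can be derived.

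**The case against.** The strongest reply has four parts.

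- **Exclusion 10 already covers the case.** A value that the protocol itself labels hepatic toxicity is an obvious use of that clause. This stands in part: most investigators might well apply it. It remains discretionary, though, and exclusion 7 may suggest that a single abnormal test is acceptable.
- **The lenient entry rule is deliberate.** Section 7.2 wants few exclusions, and 9.5.2 justifies tolerance by the 7-day course and the transient nature of the elevations. This supports keeping the two-test rule. It does not explain admitting a value above the level at which 9.5.2 ends treatment.
- **Hold and discontinue can be read as successive steps**, with 9.5.2 as the organ-specific instruction. That is reasonable, and it points to discontinuation as the action to keep. The text does not say so.
- **Monitoring is closer than Days 4 and 7.** Inpatients are assessed daily under standard of care, and the tests named in 9.5.2 are not presented as exhaustive. This is correct, so an unscheduled draw could detect the problem before Day 4.

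A reader might also infer that such a participant must be stopped on the screening value and so receive no drug. The documents do not support that. Section 9.5.1 concerns findings after enrollment, and its hepatic line appears in the list headed by new, treatment-emergent events. Other safeguards exist too: worsening counts as treatment-emergent (Protocol 11.1.4), and 9.5.1 allows stopping in the participant's best interest.

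**Conclusion.** The point holds as a minor patient-safety and consistency matter. On the text, an isolated ALT or AST above 5 × ULN passes every numeric entry criterion. If it is still above that level at an on-drug check, 9.5.2 discontinues drug; at Day 4 that is 43% to 57% of the dosing days. This rests on the value persisting, on exclusion 10 not having been used, and on reading 9.5.2 as it is written, without the treatment-emergent qualifier. The hold/discontinue conflict needs none of these assumptions and applies to anyone who crosses the limit.

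Two further inferences should be resisted. The first is that outcome data would be lost: 9.5.2 keeps the participant in follow-up to Day 60, so the Day 28 primary endpoint can still be observed. The second is a probability that such a patient enters Part 2: with no frequency in the documents, any such number would be a guess.

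**What to change.** Amend the protocol before Part 2 enrollment resumes.

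1. In exclusion 7, in both the Synopsis and 8.2.2, keep the two-test rule and add: or ALT or AST > 5 × ULN at screening.
2. Use one action for the hepatic limit in 9.5.1 and 9.5.2. Discontinuation is the natural choice because the organ-specific section already says it. The hold in 9.5.1 stays for the other toxicities.
3. State that the > 5 × ULN limit applies to every participant whatever the baseline, and that the limit of ≥ 3 × ULN for 2 days applies only to an aminotransferase that was < 3 × ULN at baseline. A stable isolated entry value of 3 to 5 × ULN then does not by itself force discontinuation.

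**Cost.** One criterion line in two places, one action word and one added statement. The amendment announced in SAP Section 10 concerns reporting of secondary endpoints, so its scope must be widened, and Protocol 15.3 requires IRB and HRPO approval. A few patients may become ineligible, against the aim in 7.2 of excluding as few as possible. Choosing discontinuation also gives up any restart after a hepatic hold. With one Part 2 participant recruited, almost no existing data are affected.
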